The primary objective of this study is to develop and pilot test an innovative cognitive self-management intervention for PwMS delivered via web-based video conferencing. Data derived from interviews will be used to guide the adaptation of Stuifbergen's 8-week Memory, Attention, and Problem-Solving Skills in MS (MAPSS-MS) intervention to be delivered via web-based video conferencing. The adapted MAPSS-MS intervention will be feasibility tested in small groups of PwMS. Outcome variables include: (1) neurocognitive function assessed using the NIH Toolbox®, a comprehensive set of psychometrically sound neuro-behavioral measures¹⁸ that quickly assesses cognitive functions using an iPad, (2) objective PA and sleep using Actigraph™ accelerometers, (3) self-reported sleep, depression, and fatigue using the Patient-Reported Outcome Measurement Information System (PROMIS), and (4) MS specific self-management using the Multiple Sclerosis Self-Management Scale (MSSM). Community-residing PwMS, age 21 to 70, will be recruited from Central Texas to participate in Phase 1 interviews (n=5) and Phase 2 pilot testing (n=20) of the adapted version of the 8-week MAPSS-MS cognitive self-management intervention emphasizing PA delivered via web-based video conferencing. In Phase 2 pilot testing (n=20), an intervention group (n=10) will be compared to an "enhanced usual care" control group (n=10).

Research Proposal

The specific aims are to:

Aim 1: (a) Conduct interviews with PwMS to gather data to guide the adaptation of a tailored, cognitive self-management intervention delivered via web-based video conferencing, (b) Develop an adapted version of the 8-week MAPSS-MS intervention guided by the analysis of the interview data.

Aim 2: Conduct a feasibility study of the adapted MAPSS-MS cognitive self-management intervention emphasizing PA using objective and self-report data from community-residing PwMS. Process outcomes include success with recruitment, ability to deliver the intervention using web-based video conferencing, and ability to measure study outcomes.

4. Procedures

Study Design

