The goal of the interviews is to acquire specific information in order to adapt the MAPSS-MS intervention. During the interviews, data collectors (the PI and a research assistant) will probe for understanding as well as summarize participant statements for accuracy. Data collectors will also keep field notes of significant ideas and interview setting. The interview transcripts will be analyzed using Miles and Huberman’s method of content analysis. The PI and one other member of the research team will initially review the transcripts. The results of the initial coding will then be reviewed by the research team and finalized. Transcripts will be analyzed for common themes regarding sessions, content, and barriers to participation. The research team will meet to review those findings and make changes to the class sessions based on the findings. The adapted MAPSS-MS intervention will not be piloted until reviewed and approved by the IRB.

Phase 2: Intervention Pilot Testing Protocol

Participants involved in Phase 1 will be invited to join the Phase 2 of the study. Additional participants will be recruited to reach the desired sample size (n=20) for Phase 2 pilot testing. Phase 2 participants will be randomly assigned to an intervention group (n=10) or an “enhanced usual care” control group (n=10). Baseline questionnaire booklets (demographic data, functional status, MS self-management, and self-report surveys) will be mailed to all Phase 2 participants upon receipt of the

Research Proposal

signed consent form and the verification of clinically definite MS form signed by their healthcare provider. At baseline and 8-weeks (post-intervention), a trained research assistant (RA) will arrange to meet with each participant individually to administer the NIH Toolbox Cognitive Battery at a location of their choice (e.g. home). At this meeting, participants will also receive an accelerometer to wear on their non-dominant wrist for 7 days and 7 nights along with printed and verbal instructions on accelerometer wear and care. The data collectors will have received training on instrument administration and accelerometry. Postage-paid, preaddressed envelopes will be given to participants to return all study materials to the PI's research office at The University of Texas at Austin, School of Nursing.

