Participants randomly assigned to the intervention group (n=10) will remotely attend eight weekly 90-minute intervention sessions from the location of their choice (e.g., home) via their chosen device (computer, tablet, and/or smart phone) using a web-based video conference platform. The 10 intervention participants will be divided into 2 cohorts of 4 to 6 persons each. Participants in the “enhanced usual care” control group (n=10) will receive an illustrated instructional booklet on Physical Activity for persons with MS developed by the National Center on Health, Physical Activity and Disability (NCHPAD).

The eight weekly educational classes, originally developed for the MAPSS-MS intervention, will be adapted for remote web-based delivery (Appendix A). Specific intervention content will be modified based on feedback from Phase 1 interviews and research team members. Content will provide educational information emphasizing PA and include: (1) information on MS self-management strategies incorporating PA, fatigue, mood, and sleep self-monitoring; (2) assessment of cognitive problems; (3) resources and barriers to self-management; (4) goal setting and self-monitoring; and (5) lifestyle changes to maximize cognitive health. Phase 2 intervention content will follow the PA guidelines specifically designed for persons with MS developed by The Canadian Society for Exercise Physiology (Ginis & Hicks, 2007). These guidelines promote fitness benefits for adults with MS who have mild to moderate disability through “30 minutes of moderate-intensity aerobic activity (e.g. walking, housekeeping, gardening) 2 times per week and strength-training exercises for major muscle groups 2 times per week” (Latimer-Cheung, Martin Ginis, et al., 2013, p. 1829). All sessions will emphasize maximizing cognitive function in MS and address the interrelated effects of PA and other self-management skills on cognitive function.

Post-intervention data (questionnaire booklets, NIH Toolbox Cognitive Battery, and accelerometry) will be gathered, using the methods described for baseline data collection, within 2 weeks of the final intervention class for those in the intervention group. Those in the control group will complete post-intervention data 8-10 weeks after baseline data collection.

a. Location

The research will be performed at the University of Texas at Austin, School of Nursing and at locations chosen by each participant (e.g., their home).

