Phase 1 interviews will be conducted by the PI at a location selected by the participant (e.g. home).

Phase 2 data will be collected by mail (U.S. Postal service) and in-person at a location of the participants' choice (e.g. home). Participants will remotely attend eight weekly 90-minute intervention sessions from a location of their choice (e.g., home) via a web-based video conference platform on their chosen device (computer, tablet, and/or smart phone).

Research Proposal

b. Resources

External funding from the Center for Transdisciplinary Collaborative Research in Self-Management Science (National Institute of Nursing Research, National Institutes of Health, Grant: P30 NR0115335: PI [name]) at The University of Texas at Austin, School of Nursing is anticipated to start 9/1/2017.

c. Study Timeline

The estimated completion time for this study is 15 months. Data collection will begin in October of 2017 and continue through September of 2018 or study completion. Data analysis will be conducted from June to August of 2018 with report writing occurring from September through November of 2018.

5. Measures

The following measures will be used to collect data on the effectiveness of the intervention at the two data collection points with the exception of demographic information and MS functional status measure, which are baseline-only measures.

Phase 1 Measures

Interview questions have been designed specifically for this project.

Phase 2 Measures

The following measures will be used to collect data on the effectiveness of the intervention. Contextual factors and MS functional status will be collected at baseline only; the remaining measures will be collected at baseline and 8-weeks post intervention.

- 1) Contextual Factors – A Demographic Information Sheet will be used to collect baseline information on a variety of demographic (age, gender, education, marital status, ethnicity) and disease characteristics that will be used to describe the sample.

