The PI and RAs have been trained in procedures to respect the rights of human subjects. There will be a special focus on issues related to 1) protecting privacy and confidentiality for participants randomized into the intervention group who will meet remotely in small groups (4-6 persons) via a web-based video conference platform on their chosen device - computer, tablet, and/or smart phone; and 2) awareness of fatigue and potential distress (related to concerns regarding cognitive and physical performance). Confidentiality and privacy of potential participants will be preserved, as the individual must contact the principal investigator to express interest in the study and disclose their name and contact information.

Research Proposal

Confidentiality of the Data or Samples

- a. Phase 1: An electronic recorder (e.g., Sony IC recorder) will be used to make electronic audio files of Phase 1 interviews. Audio files will be deleted from the recording device when transferred to UTBox cloud storage. UTBox has been approved by the Information Security Office for use with Confidential (formerly known as Category I) university data, including HIPAA data. Audio files will be named using the participant's unique ID number and the date recorded; no identifying data will be included or recorded from individual participants. De-identified audio files will be transcribed by a professional transcription service. Audio files stored on UTBox will be destroyed after they have been transcribed and the transcriptions reviewed by the PI and RA.
- b. Phase 2: After receipt of the signed consent and verification of MS diagnosis forms, participants will be mailed: 1) the questionnaire packet to complete at home with instructions (e.g., to take breaks as often as needed); 2) a postage-paid, preaddressed envelope to return the completed questionnaire packet to the PI's research office at The University of Texas at Austin, School of Nursing. A trained RA, blinded to the participant's group assignment, will collect the NIH Toolbox measures using an iPad at baseline and 8-weeks (post-intervention) at a location (e.g. home) selected by the participant. Accelerometer data will be downloaded directly from each device onto the PI's password-protected computer.

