Official Title:

A Cognitive Self-Management Intervention for Persons with Multiple Sclerosis:
Adapting Web-based Technology

Statistical Analysis Plan

Results will be entered into a computer database for analysis using IBM SPSS Statistics version 25. Data will be checked for accuracy by research staff. Reliability estimates (internal consistency) will be determined for each instrument, and alphas of >0.70 will be considered acceptable. Descriptive analyses will be performed to obtain a description of the sample on demographic and illness-related variables. Analysis of covariance (ANCOVA) will be used to measure the differences between groups while controlling for continuous variables that might affect the outcome (e.g., age, length of diagnosis). The significance level for this pilot study will be alpha <0.10 . Feasibility measures will look for trends in the data focusing on recruitment and retention of participants over the 8-week intervention, problems and solutions encountered using the web-based video conferencing platform by the interventionist and/or the participants, wear ability of the ActiGraph wrist watches for seven days.

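### Does teaching the intervention arm in two small cohorts make the ANCOVA standard error too small?

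*Protocol*

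**What the plan says.** Protocol section 4 (Phase 2) randomises individuals 1:1. The intervention arm attends eight weekly 90-minute video sessions, and "The 10 intervention participants will be divided into 2 cohorts of 4 to 6 persons each". Section 7 repeats the format, describing participants "who will meet remotely in small groups (4-6 persons) via a web-based video conference platform". A control participant "will receive an illustrated instructional booklet on Physical Activity for persons with MS" and has no group sessions.

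On analysis, the SAP states that "Analysis of covariance (ANCOVA) will be used to measure the differences between groups", adjusting for continuous variables of which age and time since diagnosis are examples. It adds that "The significance level for this pilot study will be alpha <0.10". It names no cohort term, random effect, robust standard error or ICC. It also promises no confidence interval and does not say how far beyond these participants the result should reach.

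On purpose, Aim 2 (section 3) is feasibility: "Process outcomes include success with recruitment, ability to deliver the intervention using web-based video conferencing, and ability to measure study outcomes". Section 5 nevertheless introduces the Phase 2 instruments with "The following measures will be used to collect data on the effectiveness of the intervention".

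**The concern.** This is a partially nested design: independent controls on one side, two teaching groups on the other. People who spend eight sessions together may come to resemble one another through group dynamics, attendance or how a session ran. An ordinary ANCOVA treats all 20 residuals as independent. If cohorts differ because of how delivery went, the intervention mean rests on two group-level draws as well as ten people, and the usual standard error misses the first source of variation.

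At stake would be a between-group p-value that is too small and an interval that is too narrow, in a study that calls its measures effectiveness data and sets a significance level. The estimated difference would not be biased.

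**Working it through.** The documents state no ICC, SD, effect size or power, so there is no planned figure to reproduce. The ICC and the two-sided test are assumptions.

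**Inputs.** Ten per arm, with intervention cohorts of 5+5 or 4+6 (Protocol section 4); nominal level 0.10 (SAP). Outcome variance is set to 1 in each arm. In the intervention arm a share ρ (the ICC) lies between cohorts and 1−ρ within them.

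**True variance of the difference.** 1/10 + (1−ρ)/10 + ρ·Σm²/100, where m are the cohort sizes and Σm² is 50 (5+5) or 52 (4+6).

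**Variance the unadjusted analysis reports, on average.** (2/10) × ½ × [1 + (1−ρ) + ρ(10−Σm²/10)/9].

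**Worked case, 5+5, ρ = 0.10.** True: 0.100 + 0.090 + 0.050 = 0.240, SE 0.490. Reported: 0.2 × ½ × [1 + 0.900 + 0.0556] = 0.1956, SE 0.442. Ratio: 0.490/0.442 = 1.108.

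| ICC | True SE (5+5) | Reported SE (5+5) | Ratio 5+5 | Ratio 4+6 | Rejection 5+5 | Rejection 4+6 |
|---|---|---|---|---|---|---|
| 0 | 0.447 | 0.447 | 1.00 | 1.00 | 0.100 | 0.100 |
| 0.01 | 0.452 | 0.447 | 1.01 | 1.01 | 0.103 | 0.103 |
| 0.05 | 0.469 | 0.445 | 1.055 | 1.057 | 0.117 | 0.119 |
| 0.10 | 0.490 | 0.442 | 1.108 | 1.113 | 0.135 | 0.136 |
| 0.20 | 0.529 | 0.437 | 1.210 | 1.220 | 0.170 | 0.173 |

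Rejection rates come from 400,000 simulated null trials per setting without covariates (Monte Carlo error about 0.0005). With two or three covariates unrelated to outcome they are 0.113–0.117, 0.130–0.134 and 0.157–0.167 at ICC 0.05, 0.10 and 0.20.

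**What that null means.** In these simulations the intervention has real effects in each cohort that average to zero over a hypothetical population of cohorts. If it does nothing to anyone, delivery creates no cohort variation, ρ = 0, and the test rejects at 0.100.

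**Cases with no inflation.**
- Cohorts formed by splitting on a baseline variable correlated 0.3, 0.5 or 0.7 with outcome show apparent ICCs of 0.09, 0.24 and 0.43, yet the test still rejects at 0.100. Similarity within a cohort is therefore not evidence of a fault.
- If inference is confined to these two cohorts, their effects are fixed. Opposite effects of ±d in cohorts of 5 cancel in the arm mean but enter the residual. The pooled variance becomes 1 + ½·d²·10/9, which is 1.035 at d = 0.25 SD and 1.139 at d = 0.5 SD. The reported SE is then too large by factors of 1.017 and 1.067, and simulated rejection is about 0.094 and 0.080.

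**Can the trial settle the ICC?** No. With two cohorts of 5, the ANOVA estimate has a 5th–95th percentile range of −0.25 to 0.59 when the true ICC is 0.10, and −0.25 to 0.46 when it is 0. One degree of freedom between cohorts also makes a random effect or a cluster-robust SE unreliable.

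**What an allowance would deliver.** The only workable device is to widen intervals at assumed ICCs. Without covariates, the 90% half-width is 1.734 × √0.2 = 0.78 SD. It becomes 0.82, 0.86 and 0.94–0.95 SD at ICC 0.05, 0.10 and 0.20. If the true ICC is 0, these intervals correspond to tests at 0.083–0.084, 0.069–0.071 and 0.049–0.050 instead of 0.10. Section 5 lists 16 questionnaire and cognitive scores (1 + 8 + 7) and five actigraphy sleep variables, so three ICCs give 21 × 3 = 63 extra intervals. None changes the main estimate.

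**The case for a change.** The best case for acting is that the sponsor chose to test. Section 5 speaks of effectiveness and the SAP fixes an alpha, so readers will probably see a p-value whose validity depends on an assumption stated nowhere. At an ICC of 0.20 a nominal 10% error rate is about 17%. A short paragraph would cost little, the planned ANCOVA could stay as the main result, and cohort membership has to be recorded for scheduling anyway.

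Part of this stands. The nesting is real, the SAP does not mention it, and a report that presented the p-value without saying the arm was taught in two groups would be incomplete.

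The step from there to a needed amendment does not stand. The ICCs of 0.05, 0.10 and 0.20 have no source in the documents, and the trial cannot choose among them. Whether the standard error is too small, right or too large depends on whether the two cohorts are viewed as a sample or as the study itself, on which reasonable statisticians differ. Remote attendance, individual testing and the SAP's reference to a single interventionist neither prove nor exclude a cohort effect. Multiplicity also matters more here: 21 outcomes at 0.10 give 21 × 0.10 = 2.1 expected chance positives with no clustering at all, against 21 × 0.135 = 2.8 if every outcome had an ICC of 0.10. Such p-values are exploratory with or without cohorts.

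**Conclusion.** No change to the plan. The omission is a minor reporting limitation, not an established error in the standard error. The SE is too small only if group delivery creates cohort variation and the result is carried beyond these two cohorts. Under both assumptions the shortfall is immaterial at ICC 0.01 (about 1%) and about 5%, 11% and 21–22% at 0.05, 0.10 and 0.20 without covariates. Without either one, the test is at or below its nominal level.

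Leaving the ANCOVA as written is a fair trade-off. No correction can be estimated from two cohorts, assumed corrections add intervals without changing any result, and Aim 2 is judged on process outcomes with no stated decision tied to the test. An analyst can be expected to keep the cohort identifier, note the partial nesting as a limitation, and read between-group p-values as exploratory and conditional on these two cohorts. None of that needs an amendment. The nesting would deserve explicit planning in a later trial designed to estimate efficacy.

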This pilot feasibility study employs a mixed methods design conducted in a community setting. Phase 1 uses a single-group qualitative design involving a convenience sample of 5 adults with MS; Phase 2 uses a randomized controlled trial (RCT) design conducted with a sample of 20 adults with MS (10 intervention/10 control). Phase 2 data will be collected at baseline (before the intervention) and at 8-weeks (post-intervention). Data includes self-report measures, an objective measure of physical activity, and neurocognitive tests. An “enhanced usual care” control group is selected as most appropriate for this pilot feasibility study of a non-pharmacologic, behavioral intervention.

Phase 1: Qualitative Descriptive Interview Protocol

The initial phase of this study will involve individual interviews with a purposive/convenience sample of 5 participants who have MS. After informed consent has been obtained, the PI will conduct and audio-record individual interviews lasting approximately 45 to 60-minutes with each participant meeting inclusion criteria. The interviews will include questions concerning how participants manage their MS, how they feel MS does or does not affect cognitive function, and how they feel cognitive function affects their MS self-management, as well as other MAPSS intervention topics. Additional probe questions may be used as needed to clarify responses. After interviews are completed, the audio recordings will be transcribed, and analyzed. The team will meet to make changes to the intervention based on those findings.

Qualitative Data Analysis

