Phase 2 - Participants in the intervention group will benefit by learning about MS self-management and strategies to potentially improve cognitive function. Participants in the “enhanced usual care” control group will receive an illustrated instructional booklet on PA for PwMS developed by the National Center on Health, Physical Activity and Disability (NCHPAD).

d. Risks

There is very minimal risk to participants. The anticipated risks for PwMS participating in this study are:

- 1) Breach of confidentiality and loss of privacy
- 2) Potential distress related to concerns about MS-related cognitive function and performance on cognitive testing
- 3) Physical injury (falling or tripping) and temporary increases in MS symptoms due to increased core body temperature (e.g., fatigue, numbness/tingling sensations, foot drop) that may be related to PA or environmental conditions

These risks are considered minimal and will be addressed in the study protocol. They will also be described in the consent form. Persons who participate in the study may already have concerns

Research Proposal

about their perceived cognitive function and this may be a source of distress. It is not expected that these risks will be greater than those experienced in living with the cognitive demands of everyday life. Although participants with self-reported major depressive disorder will be screened and excluded at the beginning of the study, participants with T-scores ≥ 60 ($1^+ SD$) on the PROMIS Depression instrument will be referred to their healthcare provider for further assessment and treatment.

Data and Safety Monitoring Plan

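### Randomisation is not tied to the two class cohorts, and the post-test is timed from the last class in one arm but from baseline in the other, so follow-up interval and calendar date can differ by arm

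*Protocol*

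**What the plan says.** Protocol section 4 (Study Design) describes Phase 2 as a randomised trial "conducted with a sample of 20 adults with MS (10 intervention/10 control"). Under the Phase 2 heading, "Phase 2 participants will be randomly assigned to an intervention group (n=10") and the other ten go to enhanced usual care. Later in the same section, "The 10 intervention participants will be divided into 2 cohorts of 4 to 6 persons each". The documents do not say when randomisation takes place, whether it is blocked, or whether the cohorts run side by side or one after the other.

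Three timing rules follow in that section:

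- Baseline booklets "will be mailed to all Phase 2 participants upon receipt of the" signed consent and diagnosis verification forms. The cognitive testing and accelerometer hand-out happen at individually arranged meetings. No baseline step is dated relative to a class start.
- The post-test takes place "within 2 weeks of the final intervention class for those in the intervention group".
- For the other arm: "Those in the control group will complete post-intervention data 8-10 weeks after baseline data collection".

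On the calendar, section 4c states: "Data collection will begin in October of 2017 and continue through September of 2018 or study completion". The SAP plans ANCOVA with continuous covariates, giving age and time since diagnosis as examples. It names no term for cohort, wave, calendar date or follow-up interval.

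**The concern.** Intervention participants have to wait for a class to form, and their post-test moves with that class. Controls belong to no cohort, and their post-test is counted from their own baseline. Following the plan as written can therefore give the arms different intervals between tests and different calendar dates, even though allocation is random.

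The outcomes affected are cognitive performance, accelerometer activity and sleep, and self-reported fatigue, depression and sleep. Anything that changes with time since baseline, or with time of year, would then be mixed with the group difference. Section 6d accepts that temporary symptom increases such as fatigue can have outside causes, "that may be related to PA or environmental conditions". The matter also touches Aim 2, because delivering small-group classes and measuring outcomes are among the things the pilot is meant to test.

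**Working it through.** **Inputs.** From Protocol section 4: 20 people, 10 per arm; two cohorts of 4 to 6; eight weekly classes; the two post-test rules. The wait W from baseline to first class is not given, so values of W below are assumptions.

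**1. The plan's own split.** Two cohorts of 4 to 6 hold 8 to 12 people. Ten divide as 4+6, 5+5 or 6+4, so the stated structure is consistent once ten intervention participants exist.

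**2. Interval from baseline to post-test.** With classes in consecutive weeks, the eighth falls 7 weeks after the first, that is W+7 weeks after baseline. Allowing up to 2 further weeks, the intervention window is W+7 to W+9. The control window is 8 to 10.

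| W (weeks, assumed) | Intervention | Control |
|---|---|---|
| 0 | 7 to 9 | 8 to 10 |
| 1 | 8 to 10 | 8 to 10 |
| 4 | 11 to 13 | 8 to 10 |
| 8 | 15 to 17 | 8 to 10 |

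The windows coincide at W = 1. They stop overlapping when W+7 exceeds 10, that is when W exceeds 3 weeks.

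**3. Cohort filling, under two readings of the randomisation.**

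- *All 20 assigned together, exactly 10/10.* By step 1 the cohort sizes can always be met at randomisation. The cost is older baselines. If enrolment lasts more than 10 weeks (an assumption) and baseline is taken on entry, the earliest enrolees pass the control post-test window before arms exist.
- *Assigned on entry from a 10/10 list not blocked by wave, with cohorts in sequence.* The number k of intervention participants among the first ten is hypergeometric: P(k) = C(10,k)·C(10,10−k)/C(20,10). Then P(4 ≤ k ≤ 6) = (44,100 + 63,504 + 44,100)/184,756 = 151,704/184,756 = 0.821, so the chance of falling outside is 0.179. If the first wave has 8 people, the sum is (44,100 + 30,240 + 9,450)/125,970 = 83,790/125,970 = 0.665, so 0.335 falls outside. A first wave of 12 gives the same value.

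**4. Calendar balance under the second reading, two waves of ten.** The arms differ by |2k − 10|/10 in the share enrolled in the first wave: 20 percentage points for a 6/4 split and 40 for 7/3. The expected absolute difference is (0.2×88,200 + 0.4×28,800 + 0.6×4,050 + 0.8×200 + 1×2)/184,756 = 31,752/184,756 = 0.17.

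**5. With 5:5 randomisation inside each wave of ten.** Both cohorts have 5 people, within 4 to 6, and the difference in step 4 is 0. The intervals in step 2 agree only if the control rule is changed as well.

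**The case against.** The strongest reply is that the documents are silent rather than wrong. They set no order for randomisation and cohorts; the two cohorts could run in parallel soon after baseline, with W near 1 week. Three points in that reply stand.

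- A reader might infer that all 20 are randomised in one step and that the cohorts may then fail to fill. The documents do not state a single randomisation, and if there were one, ten people could always be divided into two groups of 4 to 6.
- The 0.18 is not the chance that the trial fails its cohort rule. Nothing says a cohort closes at the tenth enrolee; a class could start at its fourth to sixth intervention participant. The figure measures how often people would have to wait or be moved. A coin-toss model would give a larger figure, but it does not guarantee the stated 10/10.
- A reader might infer that the arms will be measured in different seasons. The documents do not show this. The October to September window also holds the Phase 1 interviews, the adaptation of the classes and ethics approval before piloting. Randomisation balances entry date in expectation, and section 6d lists a participant risk, not a seasonal effect on outcomes.

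It may also be said that trouble filling classes is something a feasibility study exists to record. That is fair for the filling question. It does not answer the post-test rules, which differ by arm in the text itself and which chance balance of entry dates does not remove. Nor can later adjustment be relied on: if every intervention interval is longer than every control interval, interval and arm cannot be separated.

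**Conclusion.** The point holds in a limited form. Allocation is not tied to the class cohorts, and the post-test is anchored to different events in the two arms with no limit on the wait for a class. Follow-up interval and calendar date can therefore differ by arm. The size depends on W: no difference in window at 1 week, 3 weeks' difference at an assumed 4, and 7 weeks' difference at an assumed 8.

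The 0.18 chance of an awkward first cohort is a secondary matter. It rests on three assumptions: assignment on entry, an unblocked 10/10 list, and sequential cohorts with the first drawn from the first ten enrolled. A seasonal difference is possible but not established. For a 20-person pilot with feasibility aims the severity is minor to moderate.

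**What to change.** In Protocol section 4:

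1. Enrol Phase 2 in two waves of about ten.
2. Take baseline for the whole wave in a short window just before its classes start.
3. Randomise the wave in one step after baseline, 5 to classes and 5 to control, and start that cohort.
4. Collect post-tests for both arms of the wave in one calendar window, no later than two weeks after that wave's last class. This replaces the control rule based on each person's own baseline.

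In the SAP, state that results will be shown by wave.

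Step 4 is essential. Randomising by wave while keeping the present control rule could widen the gap: if baseline were taken on entry and a wave took six weeks to fill (an assumption), a control's post-test would fall 8 − 6 = 2 to 10 − 6 = 4 weeks after randomisation.

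The cost is protocol and SAP wording and two allocation lists, with no extra participants or staff. The downside is that early enrolees in both arms wait for their wave to fill, with some risk of losing them before randomisation. Dropout after randomisation can still take a cohort of 5 below 4 if two people leave.
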